9.5. Unscheduled visit

In case an additional visit is performed for study purposes or in case of an early termination visit outside of a normal protocol visit, an unscheduled visit can be used to report data. This visit can be conducted onsite or remotely.

Unscheduled visit procedures could include, but are not limited to:

- Insulin pump and/or CGM training
- Upload AHCL pump into CareLink. Use correct Subject ID (327-XXX-XXX).
- Upload data from the Meter in CareLink™ Personal for Clinical Research using correct Subject ID (327-XXX-XXX).
- Upload data of Transmitter using the Download utility, if used in previous weeks. Make sure to use correct file name (Subject ID_UNSCHEDEDLED_DATE). Refer to Blinded CGM Instructions for more details.
- Review adverse event or device deficiency, if any.

9.6. Early Termination Visit

Whenever possible, the study staff will perform an Early Termination visit when a subject decides to withdraw from the study early or if the subject is withdrawn early upon decision of investigator (during a normal study visit or an unscheduled visit). This visit can be conducted onsite or remotely.

Early Termination procedures:

- Upload AHCL pump into CareLink. Use correct Subject ID (327-XXX-XXX).
- Subject to complete questionnaires HFS, DTSQs, DTSQc and DQoL, if possible.
- Collect blood sample for HbA1c (central lab kit), if possible.
- Review adverse event or device deficiency, if any.
- Collect all study supplies back from subjects.

9.7. Study Exit

After the study has been completed (at Visit 13 or in case of early termination), the subjects will be exited from the study. The subjects will continue to be treated following the routine practice of each center.

9.8. Study procedures

9.8.1. Glucose and Glycemia Measurements

During the course of the study, the subjects' BG levels, SG levels, and HbA1c will be assessed using the methods outlined in this section.

9.8.1.1. HbA1c at central laboratory

A Central laboratory will be used for HbA1c testing. Refer to Lab manual for details.

All HbA1c blood specimens will be sent to and tested by a NGSP certified Central Laboratory. HbA1c testing must follow NGSP standards. The blood sample will be destroyed according to the Central laboratory procedure after analysis.

Collected at baseline (Visit 1), the first HbA1c value, will be used as screening criteria. HbA1c is also collected at 3 months (Visit 7A), 6 months (Visit 8) and 12 months (Visit 13).

9.8.1.2. Daily Blood Glucose

Values will be assessed during the study by all subjects using the CONTOUR®NEXT LINK 2.4 study meter. The control solution test will be performed following the manufacturer's user guide. Subjects will be trained on the use of the CONTOUR®NEXT LINK 2.4 study meter per the manufacturer's instructions.

9.8.1.3. Sensor Glucose Values

At baseline during the run-in phase and in the control arm during the study phase, SG data will be collected using the blinded CGM. Refer to Blinded CGM instructions and section 7.4 for more details.

In the treatment arm, SG data will be collected by subject's study pump and calibrated by subject's CONTOUR®NEXT LINK 2.4 study meter.

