7.1. General Overview of the AHCL system

The Medtronic AHCL MiniMed™ 670G system version 4.0 evaluated in this study includes investigational insulin pump and CE-marked components, which will all be used within their intended use according to the labelling and instructions for use.

The AHCL MiniMed™ 670G system, version 4.0 system is indicated for management of type 1 diabetes.

Figure 4: AHCL MiniMed™ 670G system version 4.0

CIP327 (ADAPT) Clinical Investigation Plan

10933285DOC

Version H

Page 26 of 123

Medtronic

Table 2. Status of the AHCL System components and consumables

Device name	MDT Model number	Device Status
AHCL MiniMed™ 670G Insulin Pump, version 4.0	MMT-1741 or MMT-1742	Investigational [†]
Guardian™ Sensor 3	MMT-7020	Non-Investigational / CE-marked
Guardian™ Link 3 Transmitter *	MMT 7810	Non-Investigational / CE-marked
Charger *	MMT-7715	Non-Investigational / CE-marked
Tester *	MMT-7736L	Non-Investigational / CE-marked
One-Press Serter*	MMT-7512	Non-Investigational / CE-marked
CareLink™ Personal For Clinical Research Software	MMT-7333	Non-Investigational / CE-marked
CONTOUR® NEXT LINK 2.4 blood glucose meter and CONTOUR® NEXT Test Strips by Ascensia	MMT-1151 or MMT-1152	Non-Investigational / CE-marked
Consumables and accessories	See appendix 17.6	Non-Investigational / CE-marked

[†] The insulin pump may receive CE-mark and become commercially available during the course of the study.

*Devices may be combined and distributed in kits.

Note: The Dock (T8381) and Download Utility Software (9029393) are study tools that will be used by the site staff only for sensor data collection with the Guardian Link 3 Transmitter used in a blinded mode. These tools are not evaluated during the study.

Table 3. Indicative numbers of devices per subject during the entire study

Item	Units per Subject (Treatment Arm)	Units per Subject (Control Arm)
AHCL MiniMed™ 670G Insulin Pump, version 4.0	1	1
Guardian™ Link 3 Transmitter	3	7
Guardian™ Sensor 3	84	52
One-press Serter	1	1
Reservoirs	130	70
Infusion Sets	130	70
Infusion Set Serter (if applicable)	1	1
AA Alkaline Battery	56	32
CONTOUR NEXT LINK 2.4 meter	1	1
CONTOUR NEXT Strips	3330	1990

Medtronic Business Restricted

This document is electronically controlled

056-F275, v B Clinical Investigation Plan Template

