7.4. Study tools for Blinded CGM

The Guardian™ Link 3 attached to the Guardian™ Sensor 3 will be used as a blinded continuous glucose recording system at baseline and for the control arm recording and storing SG data. The Guardian™ Link 3 transmitter will not be linked to a MiniMed™ pump, and therefore sensor data will not be transmitted to the pump. The sensor data the transmitter contains will be downloaded with the Download Utility software to a computer. The recorded and transferred sensor data are blinded and not available to subjects and healthcare professionals. Therefore, this data cannot be used for therapy adjustment during the study and will only be used to collect data at baseline and for comparison with the treatment arm during study data analysis.

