13.5. Analysis of Primary Endpoint

The primary objective is to compare the mean HbA1c change from baseline to end of study (6 month) between control arm ($\Delta_{\text{HbA1c MDI therapy + FGM}}$) and treatment arm ($\Delta_{\text{HbA1c AHCL}}$). The null hypothesis $H_0: \Delta_{\text{HbA1c MDI therapy + FGM}} = \Delta_{\text{HbA1c AHCL}}$ will be tested against the alternative hypothesis $H_A: \Delta_{\text{HbA1c MDI therapy + FGM}} \neq \Delta_{\text{HbA1c AHCL}}$ using a linear mixed model (random effect model) that uses all available data and account for possible missing at random data. This confirmatory analysis aims at demonstrating the superiority of AHCL and will be performed on the Intent to Treat (ITT) basis. The ITT population will be composed of all randomized subjects irrespective of their compliance to the planned course of treatment or deviations from protocol. Significant between arm difference will be concluded if $P\text{-value} < 0.05$.

Descriptive summary statistics of the primary endpoint will be presented stratified by study phase, treatment arm, investigational (study) site and other variables.

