13.6. Analysis of Secondary Endpoints

Analysis on secondary endpoints listed in section 5.3.2 will be performed using a linear mixed model on the ITT population. This is a confirmatory trial for primary and secondary endpoints in cohort A as described in following sequential testing. If the primary endpoint analysis is significant, the procedure tests hierarchically the ordered hypotheses in sequence at level $\alpha=0.05$ until one of the hypotheses is non-rejected.

- % Time spent in hyperglycemic range with SG > 250 mg/dL (13.9 mmol/L)
Non-inferiority test with non-inferiority margin of 6%
(the margin of 6% corresponds to approximately 90 minutes per day which is considered as a clinically relevant reduction in time spent in hyperglycemia).
- % Time spent in hyperglycemic range with SG > 250 mg/dL (13.9 mmol/L)
Superiority test
- % Time spent in hyperglycemic range with SG > 180 mg/dL (> 10.0 mmol/L)
Non-inferiority test with non-inferiority margin of 6%
- % Time spent in hyperglycemic range with SG > 180 mg/dL (> 10.0 mmol/L)
Superiority test
- % Time spent within range with sensor glucose (SG) between 70 - 180 mg/dL (3.9-10.0 mmol/L)
Non-inferiority test with non-inferiority margin of 6%
- % Time spent within range with sensor glucose (SG) between 70 - 180 mg/dL (3.9-10.0 mmol/L)
Superiority test
- % Time spent in hypoglycemic range with SG < 54 mg/dL (3.0 mmol/L)
Non-inferiority test with non-inferiority margin of 2% (the margin of 2% corresponds to approximately 30 minutes per day increase which is considered as a clinically relevant reduction in time spent in level II hypoglycemia)
- % Time spent in hypoglycemic range with SG < 70 mg/dL (3.9 mmol/L)
Non-inferiority test with non-inferiority margin of 5% (the margin of 5% corresponds to 72 minutes per day which is considered as a clinically relevant reduction in time spent in level 1 hypoglycemia).

Superiority test for % Time spent in hypoglycemic range with SG < 54 mg/dL, < 70 mg/dL and analyses on the ancillary endpoints listed in section 5.3.3 and safety endpoints listed in section 5.3.2.1, may be performed for exploratory purpose and significance of these tests will not be claimed. Linear mixed model will be used for the endpoints with repeated measures and analysis of variance will be used for single measurements.

Descriptive summary statistics will be presented for all secondary, safety and ancillary endpoints.

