13.7. Handling Missing Data

Primary endpoints and Secondary endpoints will be collected at baseline, end of 3 months and end of 6 months and primary and secondary analysis will be based on ITT (Intention to Treat).

For the primary analysis (change of A1c), if A1c at 3 months or 6 months is not available in subjects that drop-out of the study, various sensitivity analyses will be performed:

- Per Protocol Dataset
- Baseline Observation Carry Forward (BOCF)
- Data will be imputed by selected A1c data from the same arm considering baseline characteristics such as age, gender and duration of diabetes

For the secondary endpoints, as suggested by International Consensus Group (ICG), during the two weeks period of SG comparison at 3 months and 6 months between control and treatment arm, a minimum number of 2880 of SG values (288 SG values/day \times 10 days out of 14 days) is required to evaluate the glycemic outcome. For those subjects with less than 2880 SG during the two weeks of sensor wear, the following sensitivity analysis will be carried out to mitigate the impact of data loss:

- CGM data gap filled within the same subject: Missing CGM data in one arm will be imputed by randomly replaced CGM data in the same subject during the same period of sensor wear.
- CGM data gap filled within the arm, ignoring baseline characteristics: Missing CGM data will be imputed by a randomly selected CGM data from the same arm, ignoring baseline characters during the same period of sensor wear.
- CGM data gap filled within the arm, considering baseline characteristics: Missing CGM data will be imputed by selected CGM data from the same arm, considering baseline characters such as age, gender and duration of diabetes during the same period of sensor wear.

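### Treatment-arm subjects who stop the AHCL sensor but stay in the study give no further sensor glucose, so the ITT analysis of the confirmatory CGM endpoints lacks their off-device data

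*Protocol*

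**What the plan says.** Protocol 9.8.1.3 gives each arm its own source of sensor glucose after randomisation. For the run-in and the control arm: "At baseline during the run-in phase and in the control arm during the study phase, SG data will be collected using the blinded CGM". For the other arm: "In the treatment arm, SG data will be collected by subject's study pump". Section 7.4 agrees that the blinded transmitter "will be used as a blinded continuous glucose recording system at baseline and for the control arm recording and storing SG data". Table 5 marks blinded CGM training, placement, diary and upload in the study phase with C (control) only. Under Visit 4 in section 9.2, all subjects hand back their run-in transmitters.

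The analysis is meant to include everyone. Section 13.5 defines the ITT population as all randomised subjects "irrespective of their compliance to the planned course of treatment or deviations from protocol". Section 13.6 applies it to the CGM endpoints in a confirmatory fixed sequence: "Analysis on secondary endpoints listed in section 5.3.2 will be performed using a linear mixed model on the ITT population".

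Section 13.7 sets a data requirement for each two-week window: "a minimum number of 2880 of SG values (288 SG values/day \times 10 days out of 14 days) is required to evaluate the glycemic outcome". For subjects below it, three sensitivity imputations are listed. One uses the subject's own readings from the same wear period; the other two use readings from the same arm. For HbA1c, 13.7 also lists baseline observation carried forward (BOCF).

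**The concern.** Whether glucose is measured depends on use of the tested device in one arm only. A control subject who stays in the study has a blinded recording scheduled at 3 and 6 months whatever therapy is in use. A treatment-arm subject who stays but no longer wears the AHCL sensor has none, so missing data in that arm can be a consequence of stopping the treatment under test.

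The mixed model described in 13.5 uses all available data under a missing-at-random assumption. That assumption is stated for HbA1c and seems implied for the CGM endpoints. It is least plausible when data go missing because the subject left the device. The same-arm imputations share the weakness, because the AHCL readings they draw on were recorded on the device.

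At stake are the first six steps of the sequence after HbA1c: non-inferiority and then superiority for >250 mg/dL, >180 mg/dL and time in range. If stoppers do worse than users, each comparison leans towards AHCL. The direction for the two hypoglycaemia endpoints cannot be argued in the same way.

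**Working it through.** **1. Is the absence of a treatment-arm recorder deliberate?** Table 3 gives units per subject, treatment then control: "Guardian™ Link 3 Transmitter 3 7" and "Guardian™ Sensor 3 84 52". Rebuilt from the supply lists in 9.2 to 9.4:

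- Transmitters, treatment: 2 (Visit 2) + 1 (CGM start) = 3. Control: 2 + 2 + 2 (Visits 2, 7A, 8) + 1 (Visit 11A) = 7.
- Sensors, treatment: 4 (Visit 2) + 4 × 20 (CGM start, Visits 7A, 8, 12) = 84. Control: 3 × 4 (Visits 2, 7A, 8) + 2 × 20 (Visits 11A, 12) = 52.

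All four counts match Table 3, so no blinded recorder is budgeted for the treatment arm after run-in.

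**2. Does another provision supply one?** Section 9.5 allows a transmitter upload at an unscheduled visit if one was used in the preceding weeks, but no section issues one to a treatment-arm subject who stops the sensor. Section 9.6 (early termination) lists a pump upload and no blinded recording.

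**3. Do the listed imputations cover the case?** The requirement is 2880 of 288 × 14 = 4032 readings, or 71.4%. A subject off the sensor for a whole window has no readings in it, so the same-subject method has nothing to draw on. The other two methods fill in on-device AHCL values.

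**4. Size.** The documents give neither the number of subjects who stop the sensor and stay, nor the expected CGM difference. Let d be the share of the AHCL arm off the sensor at a window and Δ the on-device difference from control. If stoppers return to control level:

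- difference over all randomised subjects = (1 − d) × Δ
- overstatement from on-device data alone = d × Δ

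Inputs: 70 randomised 1:1 gives 35 per arm. The planned follow-up loss of 7.5% (13.3) serves as a reference value for d, with 20% as a high case. Δ is assumed to be 5 to 25 percentage points.

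| d | Subjects of 35 | Δ = 5 | Δ = 25 |
|---|---|---|---|
| 7.5% | 2.6 | 0.075 × 5 = 0.4 | 0.075 × 25 = 1.9 |
| 20% | 7 | 0.20 × 5 = 1.0 | 0.20 × 25 = 5.0 |

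**5. Against the 6-point margin.** To move the arm mean by 6 points, stoppers would have to differ from users by 6 / 0.075 = 80 points at d = 7.5%, or 6 / 0.20 = 30 points at d = 20%.

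**The case against.** The case depends on subjects who give up the AHCL sensor and remain in follow-up. The protocol gives no expected number and describes no such path; the exit it describes is withdrawal with an early termination visit (9.6, 9.14). Withdrawn subjects lose later sensor glucose in both arms, and the proposed recording would not reach them. This limits the size of the problem. It does not remove it, because the ITT definition expressly provides for non-compliant subjects who stay.

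Three stronger readings are tempting, and the documents do not support them:

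- **That stoppers have no glucose data.** Readings before stopping remain, possibly including a full 3-month window that the mixed model can use. A subject who leaves Auto Mode but keeps pump and sensor is still recorded (7.2). Meter values remain, and HbA1c is scheduled at Visits 7A and 8 and, if possible, at early termination.
- **That the control arm is analysed as ITT and the AHCL arm as on-treatment.** The analysis set is ITT in both arms. Control data also require staying in the study and wearing the blinded sensor. The difference lies in the pattern of missing data.
- **That no analysis can help.** Unrecorded glucose cannot be recovered, but control-based imputation would show how far the result depends on it.

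The imputations in 13.7 are labelled sensitivity analyses, not the main analysis. The supplied SAP covers only the continuation phase. Protocol 13.8 refers to a separate SAP, and the blinded CGM instructions and visit procedures tool are separate documents, so it cannot be said that handling of sensor discontinuation is absent everywhere.

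**Conclusion.** The point holds in a limited form. In the study phase, sensor glucose capture depends on wearing the AHCL sensor in the treatment arm and not on therapy in the control arm. The ITT definition calls for data on non-compliant subjects that the schedule does not collect, and section 13.7 lists no conservative CGM analysis to show the consequence.

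The expected effect is a modest overstatement of the AHCL benefit on time in range, >180 and >250 mg/dL: about 0.4 to 1.9 points at 7.5% stopping and 1 to 5 points at 20%. These figures rest on an assumed Δ of 5 to 25 points, on stoppers returning to control level, and on a stopping share the documents do not give; 7.5% is their figure for follow-up loss. Usable 3-month data from later stoppers would reduce the effect. A reader might infer that this alone could carry a non-inferiority conclusion, but at the planned loss rate the required 80-point gap makes that implausible. It matters more for the superiority steps, which have no margin, and for the reported effect size. The HbA1c primary endpoint, which opens the sequence, is not affected.

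**What to change.** 1. In 9.3, 9.8.1.3 and Table 5, offer the existing 14-day blinded recording at Visits 7A to 7B and 8 to 9 to treatment-arm subjects who remain in the study without the AHCL sensor. Include those data in the ITT analysis of the CGM endpoints. Only data collection changes.
2. In 13.7, add a conservative CGM sensitivity analysis for treatment-arm windows missing after the AHCL sensor is stopped. Use either control-arm-based imputation or the subject's own run-in blinded CGM carried forward, the latter in line with the BOCF already planned for HbA1c. This also covers subjects who decline the recording.

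Cost: a small amendment. On the control-arm supply list, each window needs two transmitters and four sensors per subject concerned. They must be reissued, because run-in transmitters are returned at Visit 4, but the subjects were trained on them in the run-in. The downsides are up to two extra two-week wears for a few subjects, some of whom may refuse a sensor they have given up, and a slightly less favourable AHCL estimate. The sensitivity analysis costs almost nothing.

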9.8.2. AHCL use

Subjects will be trained to wear the pump and CGM continuously by site staff and they need to stay as much as possible in Auto Mode (with target of $\geq 85\%$ of the time) to maximize time in range.

The recommended settings for the Auto Mode during the study are the following:

Auto Basal Target: 100 mg/dL (5.6 mmol/L)

Active Insulin Time: 2h

9.8.3. CareLink uploads

CareLink uploads of the pump will be performed at each site visit by the site staff.

Subjects will be trained to perform weekly CareLink uploads from home, following CareLink instructions.

9.8.4. Subject Blinded CGM diary

A diary will be provided to subjects with instructions on appropriate completion at the beginning of each Blinded CGM period at Visit 2, 7A and 8. The site staff will review the diary for completeness upon return by the subjects at Visits 4, 7B and 9 and report data in eCRF as needed. Refer to Blinded CGM diary for more details.

9.8.5. Creatinine Clearance

To assess renal failure as part of the exclusion criteria at screening, the creatinine clearance will be calculated based on lab test results either performed \leq 12 months before screening or performed at screening by the local lab, following local lab procedures for blood sample collection and disposition. Creatinine clearance threshold for exclusion < 30 mL/min must be calculated with the Cockcroft or MDRD equations. The sites will follow routine practice for evaluation of the creatinine clearance.

9.8.6. Patient Questionnaires

The following validated Patient Reported Outcome (PRO) questionnaires are included in this study:

- Hypoglycemia Fear Survey (HFS)
- Diabetes Treatment Satisfaction Questionnaire (DTSQ status (s) and change (c) versions)
- Diabetes Quality of Life (DQoL)

9.8.6.1. Hypoglycemia Fear Survey (HFS)

Hypoglycemia can lead to various aversive symptomatic, affective, cognitive, physiological, and social consequences, which in turn can lead to the development of possible phobic avoidance behaviours associated with hypoglycemia. The hypoglycemia fear survey (HFS) is a psychometric instrument designed to quantify this fear (Cox, 1987). The instrument has internal consistency and test-retest stability and varies with elevated HbA1c. The HFS has in most translations two subscales, the behaviour subscale and the worry subscale and has a recollection period of 6 months.

All subjects will be asked to complete the HFS at Visit 2 (Baseline); Visit 8 (at 24 weeks of follow-up), and at Visit 13 (at 12-month follow-up) which is also the end of study. In case the subject withdraws from the study early, it is important to ensure that he/she is asked to complete the HFS at the time of study exit. Data collected from the paper questionnaire will be copied by the site staff into the electronic database.

9.8.6.2. Diabetes Treatment Satisfaction Questionnaire (Status Version and Change Version)

The DTSQ has been specifically designed to measure satisfaction with diabetes treatment regimen in people with diabetes (Bradley, 1994). The DTSQ [status version (DTSQs)] is an eight-item questionnaire, in which six questions assess treatment satisfaction and the other two assess perceived frequency of hyper- and hypoglycemia (Bradley, 1994; Bradley, 1999; Bradley, 1990).

Each item is scored from 6 (very satisfied) to 0 (very dissatisfied) such that the Treatment Satisfaction scale can range from 36 (very satisfied) to 0 (very dissatisfied) and the perceived frequency of hyper- and hypoglycemia scores range from 6 (most of the time) to 0 (none of the time).

Although the DTSQs has proved highly sensitive to change, in many studies where patients are very satisfied with treatment used at baseline, the DTSQs cannot show improvements when they switch to a new treatment, even though they might be even more satisfied with the new treatment. To overcome this limitation of the DTSQs, a change version (DTSQc) has also been developed, which asks participants to rate how their current treatment compared with their previous treatment (Howorka, 2000; Bradley, 1999).

This instrument contains the same 8 items as the DTSQs version. The difference lies in the wording of the response options and instructions, which, in the DTSQc, direct the respondent to compare their experience of treatment before the study began.

The DTSQc, used in conjunction with the DTSQs, overcomes the problem of ceiling effects that are often encountered when the status measure is used alone. The DTSQc has been shown to exhibit greater sensitivity to changes in treatment than the DTSQs and is particularly valuable when ceiling effects occur (Bradley, 2007). A major advantage of the DTSQs and DTSQc is that it has been developed to be suitable for people with type 1 or type 2 diabetes using a wide range of treatments, including various methods of insulin delivery, oral medications and diet alone, and is, therefore, appropriate for use before and after patients switch between very different treatment regimens.

All subjects will be asked to complete the DTSQs questionnaire at: Baseline (Visit 2), at Visit 8 (24 weeks of follow-up), which is before the last blinded CGM period in the Control Arm and at 12 months (Visit 13), at study end.

All subjects will be asked to complete the DTSQc questionnaire at: Visit 8 (24-week follow-up) and Visit 13 (12-month follow-up).

In case the subject withdraws from the study before Visit 13, it is important to ensure that he/she is asked to complete: the DTSQs and DTSQc questionnaire at the time of study exit.

Data collected from the paper questionnaire will be entered by the investigation site into the electronic database.

